6.1.1.2 Sensitivity analyses

To assess sensitivity of the results, the primary analysis will be repeated for:

- PP population with observed cases,
- ITT with observed cases, and
- ITT with missing value treated as no improvement (worst case analysis).

Observed cases are those not missing on primary analysis.

Additionally, further sensitivity analyses will be performed with regard to image quality as assessed by the central photography vendor. The following analyses will be performed, treating assessments that are based on photographs with not approved image quality as missing:

- PP population with observed cases,
- ITT with observed cases, and
- ITT with missing values imputed by multiple imputation.

For the sensitivity analysis using multiple imputation approach, similar methods as described in section 6.1.1.1 will be performed.

For all other sensitivity analyses, results can be taken directly from the SAS proc freq output:

CCI

, where response_data is the dataset with overall improvement data per subject. The point estimate for the proportion of responders and the lower limit of the two-sided 90% Wilson CI will be used to assess sensitivity.

A sensitivity analysis will not be done, if identical to any other analysis.

6.1.1.3 Subgroup analyses

Gain or loss of ≥ 2 BMI units from screening to Day 90 will be considered a major protocol deviation. Subjects with gain or loss of ≥ 2 BMI units from screening to Day 90 will be excluded from PP population. The following subgroups will be defined by the change in body weight from screening to Day 90:

- Subjects in ITT population with gain of ≥ 2 BMI units;
- Subjects in ITT population with loss of ≥ 2 BMI units; and
- Subjects in ITT population with change of < 2 BMI units.

The primary endpoint with observed cases will be analyzed in all subgroups, as defined above, with more than five subjects. For all subgroup analyses, the improvement score over all evaluators will be treated as missing, if at least two evaluators declare a photograph as not assessable.

Frequency tables for the proportion of treated subjects with improvement in lines and wrinkles of the décolleté (primary endpoint) will be provided by age categories (\leq median age, $>$ median age), by BMI at baseline in categories (<18.5 , $18.5 - 24.9$, $25 - 29.9$, ≥ 30.0) and by site.

6.1.2 Secondary Effectiveness Endpoint

The secondary endpoint will only be assessed among subjects reconsented for extended study participation.

The secondary endpoint of the study is the proportion of treated subjects with improvement in lines and wrinkles of the décolleté by comparing photographs taken at Day 180 (post-treatment) with baseline (pre-treatment) photographs.

Each independent evaluator will assess “Improvement”, “No Improvement” or “Cannot Evaluate” between Photograph 1 (baseline) and Photograph 2 (post-baseline). Photograph 1 will be identified, and the independent evaluators will be blinded to the random distribution of treated versus untreated status of the comparator Photograph 2 (i.e., Day 180 post-treatment among treated subjects or post-baseline for untreated individuals). If photographs are declared as not assessable during the Day 180 assessment session, the evaluators will be instructed to rate the corresponding Photograph 2 as “Cannot Evaluate”.

Improvement will be declared if at least two blinded evaluators indicate “Improvement” for the comparator photograph. In case at least two evaluators declare a photograph as not assessable (i.e., “Cannot Evaluate” is ticked), the corresponding improvement score over all evaluators will be set to missing for the secondary analysis. In case one evaluator rates a photograph as “Cannot Evaluate” and the other two evaluators disagree, the overall improvement score will be set to “No Improvement”.

[figure not shown]
The proportion of subjects fulfilling the secondary endpoint will be described by frequency statistics for the ITT subset, including the one-sided 95% Wilson CI.

Missing data, including a missing secondary endpoint assessment in subjects with unacceptable, not assessable or missing photographs at baseline or Day 180, will be imputed by multiple imputation. In case of complete data, no multiple imputation will be performed and the primary analysis is based on complete data for the ITT.

Imputation is done 50 times using a fully conditional specification logistic regression method, as implemented in SAS PROC MI with statement FCS LOGISTIC, and will use the investigational site and the baseline characteristics age and BMI as informing variables. Point estimate and Wilson CI will be calculated with methods as described in Section 6.1.1.1. For implementation, SAS code similar to the statements for the primary endpoint will be used.

Similar sensitivity analyses and subgroup analyses will be performed for the secondary endpoint.

CCI

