## 11.2.1.1 Standardized 2D Photographs

For assessment of the primary effectiveness endpoint, standardized 2D photographs will be taken at the screening visit and at Day 90, at a minimum. Among reconsented subjects, additional standardized 2D photographs will be taken at Day 180. A frontal view of the décolleté is to be obtained using the camera system provided, paired with the Canfield IntelliStudio platform to standardize image capture. Standardized 2D photographs will be utilized to complete the independent photographic review

Since photographs are of critical importance as a reference measure throughout the study, the 2D photographs taken at the screening visit (Visit 1) will be reviewed and accepted by the central photography vendor prior to treatment. If a subject's screening photographs are deemed unsatisfactory by the central photography vendor, photographs will be retaken at Visit 2. Any additional photographs collected at Visit 2 must be collected prior to treatment administration. If no repeat photography is needed, the screening photographs will default to the baseline (pre-treatment) photographs and will be used for reference throughout the study.

At each site, the respective study photographers must be trained in taking standardized photographs and follow the instructions provided in a separate photography user manual. It is of the utmost importance that subjects are photographed in highly standardized positions and with the same setup (i.e., standardized distance, area, views, color standard, lighting, and background). Every effort should be made to have the same trained study personnel take photographs at every visit, and to maintain the setup of the photo studio over the course of the study, with the identical and exact fixed camera positions for the different views and light setups.

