4.2 Intent-to-Treat (ITT) Population

The Intent-to-Treat (ITT) population consists of all subjects who are enrolled.

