6.4 Special Statistical/Analytical Issues

6.4.1 Discontinuations and Missing Data

Primary and secondary effectiveness endpoints

For analysis of the primary and secondary effectiveness endpoints the following conventions will be applied: if data from the independent evaluators is completely missing (e.g., for all 3 evaluators), the multiple imputation method will be employed as described above for the primary and secondary analysis. For the worst case analysis, the subject will be analyzed as having “no improvement”.

[figure not shown]
The following procedure for incomplete data from the independent evaluators will be applied:

- If the result of two out of three evaluators is missing, the outcome of the subject will be set to missing and the multiple imputation technique will be applied for the primary analysis. The subject will not be included in the observed case analysis and for the worst case analysis, the subject will be analyzed as having “no improvement”.
- If the result of one evaluator is missing and the other two evaluators agree on the assessment “improvement” then the outcome of the subject is set to “improvement” for all analyses.
- If the result of one evaluator is missing and the other two evaluators agree on the assessment “no improvement” then the outcome of the subject is set to “no improvement” for all analyses.
- If the result of one evaluator is missing and the other two evaluators disagree, then the outcome of the subject will be set to missing and the multiple imputation technique will be applied for the primary analysis. The subject will not be included in the observed case analysis and for the worst case analysis, the subject will be analyzed as having “no improvement”.

All other effectiveness data will be analyzed as observed with no imputation of missing values. The denominator for percentages will be all subjects in the respective analysis set or population

(i.e., missing data for binary or categorical variables will be presented as a separate possible category ‘Missing’).

CCI

Adverse events

For any missing data of adverse events, a worst case strategy will be applied for all analysis tables. The intensity will be imputed by the worst intensity “severe”, the causal relationship will be imputed by the worst relationship “related”. Missing data of the outcome will be imputed by “unknown”.

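### SAP 6.1.2 leaves the Day 90 read out of the model that imputes missing Day 180 outcomes among reconsenting subjects; adding it is a minor, cheap improvement

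*SAP*

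**What the plan says.** **Who is assessed.** SAP 6.1.2 opens with the restriction: "The secondary endpoint will only be assessed among subjects reconsented for extended study participation". Protocol 9.1 and 13.4.1.2 say the same. The ten Stage 1 subjects stop at Day 90 by design (Protocol 9.1), so at most about 80 of 90 can contribute.

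**How missing outcomes are filled.** SAP 6.1.2 uses 50 imputations by FCS LOGISTIC and "will use the investigational site and the baseline characteristics age and BMI as informing variables". SAP 6.1.1.1 names the same three variables for Day 90. SAP 6.4.1 refers back ("the multiple imputation method will be employed as described above for the primary and secondary analysis") and adds no predictor. The program code is blacked out, so this rests on the readable list.

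**What is known by Day 180.** Protocol 11.1 places the reconsent request at Visit 3, which is also the primary endpoint visit. Protocol 11.2.1.1 has photographs at that visit for everyone ("standardized 2D photographs will be taken at the screening visit and at Day 90, at a minimum") and then "Among reconsented subjects, additional standardized 2D photographs will be taken at Day 180". Protocol 14.2.2 closes the database at Day 90 and again at Day 180.

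**Sensitivity analyses.** SAP 6.1.2 carries over analyses similar to those in SAP 6.1.1.2, which include observed cases and a worst case that counts missing as no improvement.

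**The concern.** Multiple imputation corrects for non-random missingness only as far as its predictors explain it. For the primary endpoint no earlier read exists, so site and baseline characteristics are a natural list. At Day 180 an earlier read does exist, of the same region, against the same baseline photograph and by the same two-of-three rule. It is likely to be the strongest available predictor.

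Suppose Day 180 reads are lost more often in Day 90 non-improvers. An imputation that ignores the Day 90 result fills the gaps at the rate of an improver-rich observed group, and the Day 180 proportion comes out too high. If reads are lost more often in improvers, it comes out too low. At stake is how the Day 180 figure is read as evidence of durability. No success criterion attaches to it.

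**Working it through.** **The plan's own figures.** None is stated for Day 180: no sample size, reconsent rate, missing-read rate or Day 90 to Day 180 association. The nearest is the Day 90 calculation in SAP section 3. It reproduces: at n = 80 both conditions need 52 improvers, and the exact binomial power at 70% is 86.3%, against at least 85% stated. It is not in question here.

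**Inputs.** From SAP section 3: 70% Day 90 improvers. Assumed: 60 reconsenters with the same 70% share (s = 0.70); Day 180 improvement q1 = 80% in Day 90 improvers and q0 = 30% in others; site, age and BMI unrelated to outcome. The true rate is then 0.7 × 0.8 + 0.3 × 0.3 = 65.0%.

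**Closed form.** With missing rates m1 (improvers) and m0 (others), the share of improvers among observed reads is

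o = s(1 − m1) / [s(1 − m1) + (1 − s)(1 − m0)],

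and the error without the Day 90 read is (q1 − q0)(o − s).

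Example, 7% and 20% missing: o = 0.651 / (0.651 + 0.240) = 0.7306; error = 0.5 × 0.0306 = +1.53 points.

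**Simulation.** 60 reconsenters, 8 sites assumed, 50 imputations, a weak normal prior on the slopes, 2,000 runs per scenario; error is measured against the complete-data proportion of the same subjects. Paired entries are without / with the Day 90 read, in percentage points.

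| Missing, improvers/others (%) | Mean missing of 60 | Closed form, 80 vs 30 | Closed form, 70 vs 55 | Simulated mean error | Root-mean-square error |
|---|---|---|---|---|---|
| 10/10 | 6.0 | 0.00 | 0.00 | −0.2 / −0.2 | 2.2 / 1.9 |
| 5/10 | 3.9 | +0.56 | +0.17 | +0.5 / +0.1 | 1.9 / 1.6 |
| 7/20 | 6.5 | +1.53 | +0.46 | +1.3 / +0.2 | 2.8 / 2.1 |
| 10/30 | 9.6 | +2.50 | +0.75 | +2.1 / +0.4 | 3.7 / 2.7 |
| 20/7 | 9.7 | −1.63 | −0.49 | −2.0 / −0.7 | 3.3 / 2.6 |

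Mirroring the fourth row (30/10) gives o = 0.49/0.76 = 0.6447 and an error of −2.76. With no association (q1 = q0) every closed-form entry is 0.

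**Other inputs.** With 70 reconsenters, 85% against 35%, and 5/20 missing, a separate simulation (6 sites, 20 imputations) gave 71.6% without and 70.1% with the Day 90 read, against a true 70.0%. With 5% missing in both groups it gave 69.8% either way.

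**Scale.** The sampling standard error is √(0.65 × 0.35 / 60) = 6.2 points. Treating the two errors as independent at 7/20, total error falls from √(6.2² + 2.8²) = 6.8 to √(6.2² + 2.1²) = 6.5 points.

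**The case against.** The strongest reply is that this matters little and is partly covered already.

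- **Existing analyses.** The worst case is a floor for the complete-data proportion. At 7/20 the observed improvers are 0.7 × 0.93 × 0.8 + 0.3 × 0.80 × 0.3 = 59.3% of reconsenters, below the true 65.0%, so overstatement is already bounded. This stands, provided the denominator is reconsenters. The observed-case figure is 0.593/0.891 = 66.5%. It carries the same error as the three-variable imputation, so it helps less.
- **Mechanism.** SAP 6.1.2 attributes missing outcomes to unacceptable, unassessable or missing photographs. Nothing ties these to Day 90 response. This stands, and it is why every non-zero bias above is conditional.
- **Availability and scoring.** A failed baseline photograph removes the Day 90 read as well as the Day 180 read. Evaluators are also told to score unassessable images as no improvement at Day 90 but as not evaluable at Day 180. Both points stand: they weaken the predictor for some subjects without making it useless, and the simulation does not model them.
- **Noise.** With the weak prior, the extra term raised root-mean-square error by less than 0.1 point when the reads were weakly related or unrelated. With a nearly flat prior the increase reached about 0.2 (2.88 to 3.06 at 10/30, no association). This stands as a cost.

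The reply limits the importance of the point. It gives no reason to prefer the three-variable model.

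**Conclusion.** The point holds as a minor, cheap improvement. The readable Day 180 model omits an earlier measurement of the same outcome that most reconsenters should have. Under the assumed inputs the resulting error is 0 to about 2.5 points in either direction, and 0 if missingness is equal or the reads are unrelated. Confidence is high in the omission and low in its size. The primary conclusion is unaffected.

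Three stronger readings are tempting, and the documents do not support them.

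- **That Day 180 outcomes are imputed for all enrolled subjects.** The endpoint wording ("The secondary endpoint of the study is the proportion of treated subjects with improvement"), the analysis set ("described by frequency statistics for the ITT subset, including the one-sided 95% Wilson CI") and the definition ("The Intent-to-Treat (ITT) population consists of all subjects who are enrolled") could suggest this. The opening sentence of SAP 6.1.2, Protocol 13.4.1.2 and the reconsent denominator in the SAP's visit-attendance table point to reconsenters. This is a matter of labelling.
- **That Day 90 response drives reconsent, or that the extra predictor would correct for it.** No passage shows that it does, or that the blinded Day 90 read is known when reconsent is requested. The added term works only within reconsenters and leaves any selection into that group untouched.
- **That a comparison of Day 90 response by reconsent status was wrongly omitted.** No readable passage plans one, but text around the Day 180 analyses is blacked out, so its absence cannot be established.

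**What to change.** In SAP 6.1.2, add the Day 90 majority outcome, as defined for the primary analysis, as a predictor in the Day 180 FCS LOGISTIC model. Where it is missing, including after a baseline-photograph failure, impute it in the same step. State that this addresses missing Day 180 reads among reconsenters and does not address selection by reconsent. The protocol-defined Day 180 population stays as it is.

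The cost is one model term and a sentence or two, on data already collected. The site merging in SAP 6.4.5 becomes slightly more likely, and root-mean-square error may rise by up to about 0.2 point if the reads are weakly related or unrelated.

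Two optional additions, on which the point does not depend:

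- Label the Day 180 estimate and its sensitivity analyses as being among reconsenting subjects, and give n.
- Tabulate Day 90 response by reconsent status in Stage 2. With 80 Stage 2 subjects and 70% improvers, reconsent of 85% in improvers against 55% in others would show 78.3% against 43.8% (gap 34.5 points, standard error 12.5). Reconsent of 75% against 65% would show 72.9% against 62.5% (gap 10.4, standard error 11.8). Such a table could reveal strong selection but could not exclude mild selection.

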6.2 Safety Endpoints

All safety evaluations will be summarized for observed values in the SP.

6.2.1 Adverse Events

All AEs will be coded according to the Medical Dictionary for Regulatory Activities (MedDRA) version in effect at the time the database is closed.

Only treatment-emergent AEs (TEAEs) will be analyzed, which are defined as AEs with onset or worsening at or after the first administration of study treatment. In this regard, an AE, with onset prior to treatment, that worsens at or after first administration of study treatment must be documented as a new TEAE with onset at the time of worsening.

An overall summary of AEs will be provided for the following:

- Any AEs;
- Any non-TEAEs;
- Any TEAEs;
- Any treatment-related TEAEs;
- Any serious TEAEs;
- Any serious treatment-related TEAEs;
- Any TEAEs leading to discontinuation;
- Any treatment-related TEAEs leading to discontinuation;
- Any fatal TEAEs, and
- Any treatment-related fatal TEAEs.

Incidence will be provided for the following classes of AEs:

- TEAEs, subjects with TEAEs and number of TEAEs by MedDRA system organ class (SOC) and preferred term (PT);
- TEAEs, subjects with TEAEs by PT;
- Non-TEAEs, subjects with Non-TEAEs and number of Non-TEAEs by SOC and PT;
- Non-serious TEAEs, subjects with TEAEs and number of TEAEs by SOC and PT;
- TEAEs by maximum severity (mild, moderate, severe), subjects with TEAEs by PT;

- TEAEs by worst causal relationship (related, not related), subjects with TEAEs by PT;
- TEAEs by worst outcome, subjects with TEAEs by PT;
- TEAEs by affected treatment area, subjects with TEAEs by PT;
- TEAEs by maximum duration (1-3 days, 4-7 days, 8-14 days, ≥ 15 days), subjects with TEAEs by PT;
- TEAEs by maximum duration and maximum severity, subjects with TEAEs by PT;
- Related TEAEs, subjects with TEAEs and number of TEAEs by PT and SOC;
- Serious TEAEs, subjects by SOC and PT;
- Related serious TEAEs, subjects by SOC and PT;
- Serious TEAEs, listing of subjects (in case of more than 15 serious TEAEs respective table by PT and SOC will be provided); and
- Related serious TEAEs, listing of subjects (in case of more than 15 related serious TEAEs respective table by PT and SOC will be provided).

All tables will be sorted by descending frequencies in Preferred Terms (within SOCs).

The duration of AEs will be calculated by the difference of start and stop day plus 1.

If a subject has more than one outcome within a PT only the worst outcome in the respective time period will be used in the frequency tables. Also on subject level, only the worst outcome category per subject in the respective time period will be counted in the frequency table. The worst outcome is defined in the following order (from best to worst):

[figure not shown]
- recovered/resolved
- recovered/resolved with sequelae
- recovering/resolving
- not recovered/not resolved
- unknown
- fatal

Moreover, incidences of TEAEs, by PT and SOC, will be provided for the following subgroups:

- Race
- Fitzpatrick Skin Types (I, II, III versus IV, V, VI).

Listings for all AEs, as well as subsets including AEs leading to discontinuation, related SAEs, and deaths, will be provided. Treatments discontinued due to pain and device deficiencies will also be listed.

CC1

CCI

Disposition of subjects

The absolute and relative frequencies for subjects' main reason for premature study discontinuation will be tabulated, based on all treated subjects. Furthermore, the number of subjects screened, the number of subjects treated, and the number of subjects in respective analysis sets will be tabulated.

Visit attendance will be presented in a frequency table for all treated subjects. For 'Subjects expected at visit', the following visits are defined as expected for all treated subjects: Screening, Day 1 (Baseline). For subjects without reconsent, all following telephone contacts and visits are expected until Day 90 or premature study discontinuation, whatever occurs first. For subjects with reconsent, all following telephone contacts and visits are expected until regular study completion at Day 180 or premature study discontinuation, whatever occurs first. In case of premature study discontinuation at a regular visit or telephone contact, not the regular visit or telephone contact is expected but either Day 90 visit (for subjects without reconsent) or Day 180 visit (for subjects with reconsent).

Percentages of 'Subjects expected at visit' will be calculated relative to the total number of subjects treated for Screening visit until Day 90 visit and relative to the number of subjects with reconsent from TC (Day 121) until Day 180 visit.

Percentages relating to 'Visit performed' and 'Visit not performed' will be calculated relative to the number of subjects expected at the respective visit. For study discontinuations, only absolute numbers will be displayed.

Protocol deviations

The absolute and relative frequencies of subjects with protocol deviations and other reasons for exclusion from analysis sets will be tabulated, based on all treated subjects.

Demographic data and baseline characteristics

Demographic data will be summarized for the SP, the ITT, and the PP. Fitzpatrick skin type will be presented by original value as well as by categories type I-III and type IV-VI.

Previous and concomitant medications and non-drug treatments

Separation of previous from concomitant medications will be done according to the start and stop date of the medication in comparison to the date of treatment. Each medication will be allocated unambiguously either to previous medication or to concomitant medication.

- Previous medication: If stop date is before start of treatment.
- Concomitant medication: If the start date is at or after start of treatment or if the stop date is at or after start of treatment or ongoing is ticked.

Previous and concomitant medications will be coded by use of the World Health Organization (WHO) whereby the version in effect at the time the database is closed will be used.

Frequencies of previous and concomitant medications will be given on the basis of various Anatomical Therapeutic Chemical classification system of the World Health Organization (ATC) code levels for the SP. Indications for concomitant medications will not be coded and will only be listed.

Non-drug treatments will be coded using MedDRA version which is in effect at the time the database is closed. Non-drug treatments will be reported by SOC and PT levels for the SP.

Medical history and concomitant diseases

Separation of medical history from concomitant diseases will be done according to the stop date of the finding in comparison to the day of treatment. Each finding will be allocated unambiguously either to medical history or to concomitant diseases.

- Medical history: If stop date is before start of treatment.
- Concomitant disease: If the stop date is at or after start of treatment or ongoing is ticked (even if it refers to a cut-off point before start of treatment).

Rules for separation of medical history and concomitant diseases for missing or incomplete dates are given in the Appendix.

Medical history and concomitant diseases will be coded using the MedDRA dictionary and reported by SOC and PT levels for the SP.

Pain pre-treatment medication

Frequency tables of pre-treatment pain medication (initial, additional, and/or administration of nitrous oxide / oxygen mixture) will be given for the SP.

Extent of exposure

A descriptive table for the number of lines by transducer, energy level, and treatment region will be produced for the SP, containing number of observed values (n obs), number of missing values (n miss), mean, standard deviation, median, quartiles, minimum, and maximum.

Frequency tables for premature treatment discontinuation and areas treated (right, left, and overall) will be given for the SP.

Vital Signs

A descriptive summary table will be presented for weight, height, and BMI by visit (i.e., Visits 1, 2, and 3 only; height will be collected at Visit 1 only).

Urine pregnancy test

Results of urine pregnancy tests will be listed.

Device deficiencies

All device deficiencies including device deficiencies for screening failures will be listed.

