#### 6.3 Potential Benefits and Risks

The potential benefit of Ultherapy on the Octave System is improvement of lines and wrinkles of the décolleté. Additionally, the results of this study may contribute to further development of the ultrasound-based, non-invasive, tissue-tightening procedure.

Potential risks associated with the use of Ultherapy on the Octave System include localized acute and/or post-procedure pain or discomfort, erythema (redness), edema (swelling), wheals, tenderness to touch, bruising, and temporary nerve effects. Pre-treatment medications proposed for use in this study can cause nausea, lightheadedness, stomach upset, and constipation (Section 10.5.1.2). The rare possibility for burns, which may or may not result in permanent scar formation, may occur if incorrect treatment technique is used (e.g., tilting transducer, poor transducer to skin coupling, incorrect line spacing, gel pockets). Some scars may respond to medical treatment. Additionally, the following AEs have been identified during routine, post-market clinical use of the Ulthera DeepSEE System: pain; burns or burning sensation; edema/swelling; nodules; bruising; fat/volume loss; neuropathy; numbness; paresthesia; palsy; paresis; speech difficulty; muscle weakness; headache; migraine; visual change; skin sagging/drooping; asymmetry; erythema; welts; hives; rash; urticaria; pruritus; blistering; scarring; discoloration; and hyperpigmentation. These AEs were chosen for inclusion in the Ulthera DeepSEE System Instructions for Use (IFU) due to a combination of their seriousness, frequency of reporting, or potential causal connection to the Ulthera DeepSEE System. However,

because these AEs are reported voluntarily from a population of uncertain size, it is not always possible to reliably estimate their frequency or establish a causal relationship with the Ulthera DeepSEE System.

In clinical trials with the first-generation Ulthera DeepSEE system, no device- or procedure-related serious adverse events (SAEs) were observed, and reported adverse events (AEs) were generally expected, mild in nature, and short in duration.[7, 15-17] Long-term follow-up studies confirmed the favorable safety profile of the Ulthera DeepSEE system with primarily mild, treatment-related side effects.[10]

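### The subject-level row of the worst-outcome table can undercount sequelae and unresolved events, because SAP 6.2.1 ranks sequelae below open outcomes and lets an imputed unknown outrank both

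*SAP*

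**What the plan says.** SAP 6.2.1 includes this item among its incidence tables: "TEAEs by worst outcome, subjects with TEAEs by PT". Three rules govern it.

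- **Ranking.** "The worst outcome is defined in the following order (from best to worst". The list starts with recovered as the best outcome, passes through sequelae, then recovering, then not recovered, then unknown, and ends with fatal as the worst. No reason is given for the order.
- **Counting within a PT.** "If a subject has more than one outcome within a PT only the worst outcome in the respective time period will be used in the" tabulations.
- **Counting per subject.** "Also on subject level, only the worst outcome category per subject in the respective time period will be counted in the frequency table".

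SAP 6.4.1 adds a rule for blanks, under an approach it describes as worst-case: "Missing data of the outcome will be imputed by" the category unknown, which is the second-worst rank.

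Protocol 12.1.5 has the same six categories. It lists sequelae after not recovered and just before fatal, but does not call the list a ranking and does not define the categories. Protocol 13.4.2.1 does not ask for a worst-outcome table; the SAP adds it.

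**The concern.** A worst-outcome table should keep the least favourable thing known about each subject. Under this order, an event that ended with residual harm is treated as milder than one that is still recovering, such as a fading bruise. The table covers all TEAEs, so an unrelated open event can displace device-related sequelae in the subject-level row.

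The rule for blanks can work against its own purpose. An empty outcome field on a trivial event becomes unknown, and that outranks a known not recovered or a known sequelae outcome elsewhere in the same subject.

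Lasting harm matters in this study. Protocol 6.3 says that burns are a rare possibility "which may or may not result in permanent scar formation", and lists neuropathy, palsy, scarring and fat or volume loss from post-market use of the earlier system. The study objective includes demonstrating safety. None of the ten items in the SAP 6.2.1 overall AE summary counts sequelae or unresolved events, so no other summary in the visible text would correct a low count.

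**Working it through.** The plan states no figure for this point, so there is nothing to reproduce. The check applies the SAP 6.2.1 rules to a subject with one TEAE that recovered with sequelae and a second TEAE of each possible outcome. The subject-level rule is read as one category over all of the subject's TEAEs.

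| Outcome of second TEAE | Same PT: PT row | Same PT: subject row | Different PT: row of the first event | Different PT: subject row |
|---|---|---|---|---|
| recovered | sequelae | sequelae | sequelae | sequelae |
| with sequelae | sequelae | sequelae | sequelae | sequelae |
| recovering | recovering | recovering | sequelae | recovering |
| not recovered | not recovered | not recovered | sequelae | not recovered |
| unknown, or blank and imputed | unknown | unknown | sequelae | unknown |
| fatal | fatal | fatal | sequelae | fatal |

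Three results follow.

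1. Any second event that is recovering, not recovered or unknown removes sequelae from the subject-level row. So does a fatal event, but there the displacement is proper.
2. The PT row loses sequelae only when both events share the PT.
3. By the same ranking, a known not recovered event beside a blank one reads unknown in the subject-level row, and also in the PT row if the PT is shared.

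**Size in the subject-level row.** The documents give no rate of sequelae and no rate of second events, so the inputs are assumptions apart from the planned enrolment of about 90 (Protocol 13.1).

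- Assume 2 of 90 treated subjects have an event with sequelae: 2/90 = 2.2%.
- Let q be the chance that such a subject also has an outranking TEAE, independently between the two subjects.
- Chance that at least one is lost = 1 − (1 − q)².
- Chance that both are lost, so that the row reads 0/90 = q².

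| q | At least one lost | Both lost |
|---|---|---|
| 0.10 | 1 − 0.90² = 19% | 0.10² = 1% |
| 0.25 | 1 − 0.75² = 44% | 0.25² = 6% |
| 0.50 | 1 − 0.50² = 75% | 0.50² = 25% |

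These chances concern the subject-level row only. Loss from a PT row needs a second event of the same PT.

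**The case against.** The strongest reply is that little is actually hidden.

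- **The table is by PT.** A reader might infer that sequelae vanish from the whole outcome table whenever the subject has another open event. They do not. A scarred burn together with a bruise that is still recovering are two PTs, so the burn row still shows sequelae. A table with no sequelae at all, when some occurred, would need every such event to be outranked by another event of the same PT in the same subject. This part of the reply stands in full.
- **Other outputs show lasting harm.** All AEs are listed. Permanent impairment of a body structure or function resulting from serious deterioration in health is an SAE under Protocol 12.2, so it enters the serious TEAE outputs. TEAEs are also tabulated by maximum duration and severity. This stands, but these outputs do not give a count of subjects by outcome.
- **Sequelae is not the only category for lasting harm.** The categories are not defined, and the documents do not say how a scar would be recorded. One still present at the last visit might be entered as not recovered, which already ranks worse. This stands.
- **The order has a logic.** Closed events rank below open ones, whose final outcome may yet be worse, and a high rank for unknown fits a worst-case approach. The first part is a fair convention. The second fails where an imputed unknown replaces a known unfavourable outcome.
- **Blanks should be few.** Outcome must be recorded (Protocol 12.1.2), unpopulated fields raise automatic queries, and the database closes only after queries are solved (Protocol 14.2.2). This makes the imputation route less likely, but leaves displacement by recovering or not recovered untouched.

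**Conclusion.** The point holds for the subject-level row, and for a PT row only when the outranking event has the same PT. Following the rules exactly can understate how many subjects had sequelae, and a blank outcome can hide a known unresolved event.

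The point is minor. It concerns one descriptive table that feeds no decision rule. The secondary safety endpoint is the incidence of related TEAEs, which the ranking cannot change, and the primary analysis does not use it. A reader might infer that the study's safety conclusion is compromised; the documents do not support that.

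The sizes above rest on the assumed 2 of 90, the assumed range for q, and independence between the two subjects. Losing at least one subject from the row is plausible across that range. Losing both is much less likely, at 1% to 25%. That a subject-level count can be displaced does not depend on these assumptions; it follows from the rules.

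**What to change.** Make two changes in SAP 6.2.1, with a matching line in 6.4.1.

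1. Add to the overall AE summary, independent of the ranking, the number of subjects with any TEAE whose outcome is recovered/resolved with sequelae and, separately, the number with any TEAE not recovered/not resolved at last contact. Give both again for related TEAEs. That makes four rows.
2. Take unknown out of the ranking and show it separately, with recorded and imputed unknowns distinguished, so that it cannot override a known not recovered or a known sequelae outcome. Removing it is cleaner than moving it down: placed below sequelae in the present order, it would also fall below recovering. A footnote should say that a subject can appear both in a ranked category and in the unknown count.

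Ranking sequelae above recovering is optional once these counts are shown. If the present order is kept, one sentence giving the reason would help.

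The cost is a few table rows and some SAP wording. Outcome and causal relationship are already collected for every AE, so neither the eCRF nor the visits change.
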